## 9.1 Data confidentiality

All data will be stored on Penn Medicine Computing Services Servers. The Penn Medicine Academic Computing Services (PMACS): PMACS will store all data securely. The data center is housed in Information Systems and Computing at [name]. All data for this project will be stored on the secure/firewalled servers of the PMACS Data Center, in data files that will be protected by multiple password layers. These data servers are maintained in a guarded facility behind several locked doors, with very limited physical access rights. They are also cyber-protected by extensive firewalls and multiple layers of communication encryption. Electronic access rights are carefully controlled by UPenn system managers. This multi-layer system of data security, identical to the system protecting the University of Pennsylvania Health Systems medical records, greatly minimizes the risk of loss of privacy.

Patient medical record data: electronic medical record data will be extracted from patient medical records (EPIC) via a report created by the Data Analytics Center (DAC) at Penn Medicine. The report will run weekly and be placed in a folder in a PMACs or UPHS secure shared drive. This DAC report has already been created by staff on the Penn Medicine COVID-19 Registry team. The Penn Medicine COVID-19 Registry team will provide support for this project and their staff will access the report to save data points needed for this project in a different file described below. Access to this DAC report is limited to those with institutional approval to access the report. Approval is granted only for staff with HIPAA and CITI training. The file created by the Penn Registry team for this project will be saved onto a secure PMACs or UPHS drive only accessible by the team on this protocol (via password protection) or using the Penn Secure Share encrypted document sharing mechanism. The file will then be saved to a secure shared drive on PMACs server for staff access. The file will be saved with password protection and only those staff who need access to the file will be provided the password. The limited dataset will remain on this secure shared drive until the follow-up data collection and analysis is complete. Participants will be assigned a STUDY ID listed on the DAC report to match data from other sources (i.e. Way to Health).

Way to Health data: Any datasets and computer files are referred to by study ID. The study ID is also used on all analytical files. All personal information that the participant is asked to provide will be collected via Penn's Way To Health study platform. Way To Health collects subjects' names and phone numbers. They also request the name and phone number of an alternate contact. To assure that participant confidentiality is preserved, individual identifiers are stored in a single password protected system that is accessible only to study research, analysis and IT staff. An investigator or statistician who logs in will be able to access only non-identifiable data. The Way To Health administrative group and research coordinators responsible for contacting participants for follow-up study visits or responding to questions about the study are able to view participant names and contact information. The WTH web development team and Project Director currently have administrative access to PHI. All of these personnel will have completed Human Subjects Protection and HIPAA privacy training. The system automatically generates logs of all data queries which can be reviewed by research staff to ensure that no unauthorized persons have gained access to identifiable information. This system is hosted on site at The University of Pennsylvania and is protected by a secure firewall and several layers of operational security. Once a participant has been entered into this system, they are given a unique study identification number (ID). Any datasets and computer files that leave the firewall are stripped of all identifiers and individuals are referred to by their study ID. The study ID is also used on all analytical files. The Penn Medicine Academic Computing Services (PMACS) is the hub for the hardware and database infrastructure that supports the project and the Way To Health web portal is built on this infrastructure. The data collected for Way To Health based studies is

stored in mySQL databases on a PMACS-operated blade server environment devoted specifically to Way To Health. Every SQL transaction, including accessing and changing data, is logged for auditing purposes. Data are entered into the database through several different mechanisms. Participants enter their own personal information and respond to surveys through a PHP-based web interface. Researchers have a separate interface that allows them to manually enter data if needed. Datasets are stripped of all personally identifiable information when exported for analysis. The web application automatically removes all identifiers when a researcher requests an analytic dataset. The only people with access to identifiable participant information are pre-specified Research Coordinators responsible for contacting participants for follow-up. Personal information and research data will be stored in separate SQL tables and will be linked by a computer-generated ID number. Additionally, any information that leaves this system to communicate with third party data sources (i.e., survey software) is stripped of any identifiers and transmitted in encrypted format.

## **9.2 Subject confidentiality**

All participant data will be through COVID Watch or the electronic medical record. There will be no paper records or other forms of data collection. Therefore, subject confidentiality will be maintained through the data protections described above in section 11.1.

## **9.3 Subject privacy**

All data abstracted from the medical chart will be placed onto PMACS servers, all text responses will be secured on the Way to Health platform and no one but the PI, project manager, and study staff responsible for the will have access to these databases. Participants are educated about best practices for mobile phone privacy upon enrollment into the program. Patients are encouraged to contact a medical provider via telephone to discuss escalating symptoms or other symptoms they wish to speak about privately.

## **9.4 Data disclosure**

Research data will not be shared with anyone outside of the University of Pennsylvania.

## **9.5 Data safety and monitoring**

The researchers will form a Data Safety Monitoring Board only if the Penn IRB requests or recommends it.

### **9.5.1 Research Materials and Maintenance of Data Security**

The study involves data collected with protection of confidentiality. Study and survey data collected during the baseline and subsequent visits will be kept electronically secure as described in the Data confidentiality above. No one but the PI, project manager, and study staff responsible for the follow up will have access to these files. Any data used for results will only be presented in a de-identified manner in the aggregate.

### **9.5.2. Study Monitoring**

All protocols and consent forms belonging to this project will be fully approved by the IRB before implementation. The Co-PIs ([name] and [name]), co-investigators, the project managers, and others will monitor study accrual, data quality and adverse events continuously.

### **9.5.3. Monitoring Procedures**

The researchers will form a Data Safety Monitoring Board only if the Penn IRB requests or recommends it.

If the researchers are requested to form a DSMB, authority for monitoring data and safety will reside exclusively with an independent external DSMB in collaboration with the study statistician and one patient investigator (non-voting members); ultimate responsibility for the conduct of this study will reside with the CO-PIs ([name] and [name]). Written standard operating procedures and standard best practices regarding the protection of Human Subjects will be used to guide the training of involved research staff and the enrollment and interventions with subjects during and after their clinical visit.

### **9.5.4. Data Management**

The project managers ([name] and [name]) will oversee data management and management procedures will be developed and monitored by the CO-PIs ([name] and [name]). The project managers will conduct monthly quality assurance on the various data streams to ensure consistency and validity. They will make the PIs aware of any missing data and/or issues with data collection, storage, or management.

### **9.5.5. Unanticipated Problems**

All unanticipated problems related to the treatment or assessment sessions will be reported to the primary PI for the duration of the study. The PI is responsible for identifying potential unanticipated problems experienced by study participants, adjusting the intervention accordingly and reporting the experience.

## **9.6. Risk/Benefit Assessment**

### **9.6.1 Potential study risks**

Patients with COVID-19 may have quickly deteriorating health conditions. Penn Medicine OnDemand was created to ensure patients have access to COVID-19 related clinical support 24/7. Patients enrolled in COVID-Watch are monitored by Penn Medicine OnDemand and patients who report escalated symptoms are instructed to go to the Emergency Department or contacted by a clinician within an hour.

There is a risk of breach of confidentiality for participants, as they participate in the COVID-Watch programs through their personal mobile phones. As with all forms of electronic communication there is risk that information may not remain confidential through individual access. All participants have been made aware of this through the enrollment process, and participants are notified how to unenroll at any time if they feel they or their data are not safe.

Additionally, there is a risk of breach of confidentiality of data extracted from patient medical records. The steps taken to mitigate this risk are provided in the Data Management section. Only those on the research team will have access to the Way to Health platform study page and will need to sign in with their unique username and password to access records. Way to Health is maintained on secure PMACS servers that are encrypted.

### **9.6.2 Potential study benefits**

There is a direct benefit to patients that enroll into the COVID-Watch program. Patients enrolled into the program will have constant monitoring of their symptoms and a direct pathway to escalation of care if warranted by their care team. There is also an indirect benefit for patients, as this builds a network of rigorously and academically tested telemedicine for patients that have historically and disproportionately had lower access to care, while having higher rates of underlying chronic illness.

#### **9.6.2.a. Importance of the knowledge to be gained**

There is a lack of evidence and rigorous evaluations regarding telemedicine. Knowledge gained from this research could optimize how providers interact with patients that have traditionally had lower access to care. Traditional in-person ambulatory care visits risk spreading infection. The efficacy of telemedicine must be analyzed, as the pandemic has caused an exponential increase in its use to ensure patients are receiving proper care through this transition.

### **9.6.3 Risk/benefit assessment**

This study is minimal risk.

## **10. Investigators**

Principal investigators: Overall responsibility for protocol development, intervention development, budget overview, data dictionary development, ethical approval, trial registration, trial oversight, and the data and safety monitoring board, assessment of overall recruitments, potential, data analysis, and dissemination and presentation of results.

Co-Investigators: Also, protocol development, data dictionary development, trial oversight, dissemination of results.

### C. Summary of Amendments and Clarifications to Protocol

There were four modifications to the protocol. First, the researchers corrected the care escalation algorithm based on peripheral oxygenation saturation (SpO2) levels to more accurately reflect the original design and operating procedures of the COVID Watch + Pulse Oximetry program. Patients with a decrease in SpO2 by 3 or more percentage points to a level below 95% or with a reading below an absolute value of 90% triggered a care escalation alert to COVID Watch telemedicine clinician team.

Second, prior to randomizing the first participant, the researchers updated study eligibility criteria to include hospitalized patients who were initiated on COVID Watch as part of routine discharge care and exclude any patient already participating in an alternate monitoring program. The rationale for this change was that this design enabled the comprehensive capture of all patients initiated on COVID Watch and more accurately reflect the COVID Watch program's standard operating procedures.

Third, the researchers simplified the patient survey emotional distress and anxiety measure. This modification was also performed prior to randomizing the first patient. The rationale for this change was based on the feedback the researchers received from the community and patient stakeholder advisory committee.

Lastly, the researchers increased the sample size. The rationale for this change was due to a lower-than-expected COVID positivity rate and standard deviation in Days Alive Out of Hospital (DAOH) based on baseline COVID Watch program data through November 30, 2020.

Protocol Version	Amendment or Clarification	Dates
Final	Sample size was increased based on analysis of baseline data prior to trial (see amendment to statistical analysis plan)	12/17/20
	Patient survey emotional distress and anxiety measure was simplified to a single-item anxiety measure	11/02/20
	Eligibility criteria were updated to include hospitalized patients who were initiated on COVID Watch as part of routine discharge care and exclude any patient already participating in an alternate home monitoring program	11/02/20
	Care escalation algorithm based on peripheral oxygenation saturation (SpO 2 ) corrected to reflect original COVID Watch + Pulse Oximetry program design and operation	11/02/20
Original	The approved IRB protocol was considered the original protocol. Approval was granted 10/8/20.	10/08/20

#### **D. Original Statistical Analysis Plan**

The primary analysis will be an intention to treat analysis among randomized patients with confirmed COVID-19. The researchers seek to enroll at least 259 Black or Latino patients in each arm to achieve 90% power to detect a mean difference of 2 DOAH, assuming a type I error rate of 0.05. Given that Black and Latino patients comprise 61% of the COVID Watch sample, this indicates a target minimum sample size of at least 850 patients with confirmed COVID-19.

Linear mixed effects models will be used to assess the incremental effect of home pulse oximetry on DAOH relative to COVID Watch alone. Random intercepts will be used to account for clustering by testing site. Randomization will theoretically ensure balance of measured and unmeasured covariates between arms. Factors deemed to be associated with the outcome a priori will be adjusted for to increase efficiency. These include: age, sex, race, ethnicity, insurance, median income of residential ZIP code and ED vs. outpatient enrollment.

The researchers will examine heterogeneity in treatment effects using interaction terms by treatment comparator group and: the following (1) location of enrollment (outpatient vs ED); (2) primary care in the health system (yes or no); (3) insurance (none/Medicaid/Medicare/private); and (4) race/ethnicity, including an evaluation of Black and Latino patients separately. A sensitivity analysis will be performed to compare outcomes to UPHS COVID-19 patients not enrolled in COVID Watch using a propensity score analysis. The researchers will record and report all reasons for dropout and missing data, and account for all patients in reports. Because this research is being conducted in the context of routine care and COVID Watch requires a working cell phone, the researchers anticipate fewer losses to follow-up than is typical.

As secondary analyses, the researchers will repeat the above analyses in the full population of randomized patients now including the population of patients placed into COVID Watch who had suspected COVID-19 but ended up having negative COVID-19 tests.

## E. Final Statistical Analysis Plan

The primary analysis will be an intention to treat analysis among randomized patients with confirmed COVID-19. The researchers seek to enroll at least 204 Black or Latino patients in each arm to achieve 90% power to detect a mean difference of 1 DOAH, assuming a type I error rate of 0.05. Given that Black and Latino patients comprise 61% of the COVID Watch sample, this indicates a target minimum sample size of at least 1078 patients with confirmed COVID-19.

As the primary analyses, the researchers will use an intention-to-treat approach. The researchers also performed a per protocol analysis including only those patients who actively participated on their allocated protocol (e.g., responded to at least one text-message check-in). For both analyses, the researchers compared mean DAOH between study groups using two-sample t-tests. Adjustment for covariates via regression was not deemed necessary as all sociodemographic and clinical characteristics were well balanced between arms. The researchers also compared continuous secondary outcomes including mean number of outpatient visits, emergency department encounters, and hospitalizations using t-tests. The researchers compared categorical secondary outcomes using Fisher's Exact test. A prespecified subgroup analysis was completed by comparing outcomes for Black and Hispanic patients to White patients. Exploratory subgroup analyses were conducted for age strata and enrollment context (inpatient, outpatient, and ED). All tests were two-sided and a p-value  $< 0.05$  was considered statistically significant in the primary analyses. In subgroup analyses, to account for multiple testing, Bonferroni corrected p-value cut-offs are provided for the results in the supplementary tables. All analyses were conducted using R statistical software version 3.6.0 (R Foundation for Statistical Computing, Vienna, Austria. URL <https://www.R-project.org/>).

[Below is from original SAP]

Linear mixed effects models will be used to assess the incremental effect of home pulse oximetry on DAOH relative to COVID Watch alone. Random intercepts will be used to account for clustering by testing site. Randomization will theoretically ensure balance of measured and unmeasured covariates between arms. Factors deemed to be associated with the outcome a priori will be adjusted for to increase efficiency. These include: age, sex, race, ethnicity, insurance, median income of residential ZIP code and ED vs. outpatient enrollment.

The researchers will examine heterogeneity in treatment effects using interaction terms by treatment comparator group and: the following (1) location of enrollment (outpatient vs ED); (2) primary care in the health system (yes or no); (3) insurance (none/Medicaid/Medicare/private); and (4) race/ethnicity, including an evaluation of Black and Latino patients separately. A sensitivity analysis will be performed to compare outcomes to UPHS COVID-19 patients not enrolled in COVID Watch using a propensity score analysis. The researchers will record and report all reasons for dropout and missing data, and account for all patients in reports. Because this research is being conducted in the context of routine care and COVID Watch requires a working cell phone, the researchers anticipate fewer losses to follow-up than is typical.

As secondary analyses, the researchers will repeat the above analyses in the full population of randomized patients now including the population of patients placed into COVID Watch who had suspected COVID-19 but ended up having negative COVID-19 tests.

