## B. Final Study Protocol

### 1. Abstract

The clinical guidance for 90 percent of infected COVID-19 adult patients who do not meet eligibility for inpatient admission is to self-isolate. To support these patients, alternatives to in-person care are needed to manage an unpredictable clinical course; identify and intercept patients rapidly deteriorating at home, prevent viral spread during in-person visits; and minimize future surges in emergency departments (EDs). In addition, fingertip pulse oximeters have been proposed to improve in-home early detection of respiratory deteriorations but are untested and the operational infrastructure to support large-scale monitoring is limited.

While telemedicine has been widely adopted during the pandemic as an alternative to conventional outpatient care, limited telemedicine access may be exacerbating observed disparities for Black and Latino patients. In the health system, Black and Latino patients used video-visits 15 percent less often than white patients. Text messaging and phone calls may improve healthcare access for communities of color, but the evidence for these telecommunication modalities to be effective and improve equity are limited.

The University of Pennsylvania Health System (UPHS) developed and deployed COVID Watch to improve access to health care for COVID-19 patients who are self-isolating at home. COVID Watch sends twice-daily, scheduled text messages to assess patients for shortness of breath using a clinical algorithm to determine whether patients need an urgent escalation to a team of dedicated, on-call nurses within one hour. These nurses are supported by an on-call team of clinicians who can conduct urgent phone or video assessments. Patients can also trigger the algorithmic assessment independent of the scheduled messages. As of May 21, 2020, COVID Watch has managed 3,628 COVID-19 patients at home, of which 1,295 are confirmed COVID-19 positive; of these, 61 percent are Black or Latino, higher than the proportion of all UPHS COVID-19 positive patients that are Black or Latino (55 percent).

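### The final SAP's total of 1078 confirmed patients does not follow from its own inputs: 204 Black or Latino patients per arm at a 61% share gives 669

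*Combined protocol and SAP*

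**What the plan says.** Section E, the final SAP, builds its target in two sentences. It asks for "at least 204 Black or Latino patients in each arm to achieve 90% power to detect a mean difference of 1 DOAH", at a type I error rate of 0.05. It then scales up by the share of these patients in the programme, which it puts at 61%, and concludes that "this indicates a target minimum sample size of at least 1078 patients with confirmed COVID-19". Section 6 of the final protocol gives 1078 as the enrolment target by reference to the same estimate, without saying that these are confirmed cases.

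Section D, the original SAP, has the same two sentences with different numbers. It asks for "at least 259 Black or Latino patients in each arm to achieve 90% power to detect a mean difference of 2 DOAH", applies the same 61%, and concludes that "this indicates a target minimum sample size of at least 850 patients with confirmed COVID-19".

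The Abstract of the final protocol shows where a 61% share occurs: "1,295 are confirmed COVID-19 positive; of these, 61 percent are Black or Latino". It also gives 55% as the share among all of the health system's positive patients.

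The amendment summaries (Sections C and F) attribute the increase to lower-than-expected positivity and a lower-than-expected standard deviation (SD) of days alive and out of hospital (DAOH). They give no value for either. No section gives a loss allowance, and the part of Section E carried over from the original SAP says that "the researchers anticipate fewer losses to follow-up than is typical".

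**The concern.** The per-arm requirement fell from 259 to 204 and the share stayed at 61%, yet the confirmed total rose from 850 to 1078. With the share fixed, the total has to move in the same direction as the per-arm number. Either one of the stated inputs is not the one used, or a step has been left out, or 1078 carries the wrong label.

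The label matters because the primary analysis is restricted to randomised patients with confirmed COVID-19. A target of 1078 confirmed patients and a target of 1078 randomised patients are different commitments, with different consequences for power in Black or Latino patients, the group on which the calculation is based. As written, a reader can check whether 204 per arm was reached, but cannot tell what total the plan required.

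**Working it through.** **Inputs.** From Section E: 204 Black or Latino patients per arm, share 61%, difference 1 day, 90% power, alpha 0.05 two-sided, stated total 1078. From Section D: 259 per arm, share 61%, difference 2 days, stated total 850.

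**1. Reproduce the original SAP.** Confirmed total = 2 × n per arm / share.
2 × 259 / 0.61 = 518 / 0.61 = 849.2, stated as 850. This is therefore the plan's own method.

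**2. Apply the same step to the final SAP.**
2 × 204 / 0.61 = 408 / 0.61 = 668.9, so 669, against 1078 stated.
Excess: 1078 − 669 = 409 patients; 1078 / 668.9 = 1.61, so 61% too high for these inputs.

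**3. Look for the missing input.** Each line below is solved backwards from 1078. Only the 55% share is a figure in the documents.
- 1078 counts all randomised patients, 61% share: positivity 668.9 / 1078 = 62%.
- 1078 counts confirmed patients: share 408 / 1078 = 38%.
- 55% share and 1078 randomised: 408 / 0.55 = 741.8; positivity 741.8 / 1078 = 69%.
- Loss allowance: 1 − 668.9 / 1078 = 38%, although the plan expects few losses.

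Other routes also miss:
- A 55% share alone gives 742.
- Separate targets of 204 Black and 204 Latino patients per arm give 816 / 0.61 = 1338.
- Bonferroni-adjusted alpha from 0.025 to 0.0125 gives 791 to 912.
- The only ratio of confirmed to enrolled patients in the documents, 1,295 / 3,628 = 36% (to May 21, 2020), gives 668.9 / 0.357 = 1874.

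**4. See whether the amendment's reasons supply the step.** No SD is stated, so I back-solve it from a two-sample comparison of means (normal approximation, 1.960 + 1.282 = 3.2415): SD = difference × √(n/2) / 3.2415.
- Original: 2 × √(259/2) / 3.2415 = 7.02 days.
- Final: 1 × √(204/2) / 3.2415 = 3.12 days.

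At the final implied SD, a 2-day difference needs about 51 per arm, and halving the difference multiplies this by 4 to give 204. Together the two changes take the per-arm number from 259 down to 204, so they cannot raise the confirmed total. Lower positivity raises the number to be randomised, not the number of confirmed patients needed.

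**5. What each reading of 1078 implies, at the implied SD.**
- Confirmed, 61% share: 1078 × 0.61 / 2 = 329 Black or Latino patients per arm; power for 1 day about 98%.
- Randomised: 204 per arm in that group needs at least 62% confirmed (61% share) or 69% (55% share). The analysis of all confirmed patients keeps 90% power down to 408 / 1078 = 38% confirmed, if the same SD applies to them.

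**The case against.** The best defence has four parts.

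- **Both figures are floors.** At a 61% share, 1078 confirmed patients would more than satisfy 204 per arm, so the two minimums can hold together, and on the literal reading the trial is oversized. This stands as far as it goes. What fails is the claim that the first figure leads to the second.
- **The amendment summaries name lower positivity, and Section 6 omits the word confirmed.** A randomised total with the wrong label is a simple explanation. It is plausible, but the evidence is thin: Section 6 of the original protocol also omits the word for 850, which does match the confirmed total. If the explanation is right, the label in Section E is wrong and the positivity rate is unreported, so a correction is still needed.
- **Section E ties the 61% to the COVID Watch sample, not explicitly to confirmed patients.** True, but the Abstract reports 61% among confirmed patients, and the original SAP goes straight from 518 to 850 confirmed with no positivity step.
- **The SDs and power figures are back-solved.** Correct. They rest on an unclustered two-sided comparison. The central result, 669 against 1078, does not depend on them.

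It can also be said that no shortfall is shown and that Section E already describes analyses in the past tense, so a correction improves the record and not the conduct of the trial. That limits the consequences; it does not make the stated total correct.

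**Conclusion.** The concern holds. From the final SAP's own inputs the confirmed total is 669, not 1078: a gap of 409 patients, or 61%, which rounding cannot explain and no figure in the documents bridges. This needs no assumption beyond the plan's own scaling step, which the original SAP confirms.

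The documents do not show whether the share, the per-arm number, the label or the total is the wrong one, so 669 is what the inputs give and not necessarily what was intended. Underpowering is not demonstrated. Read literally, power in Black or Latino patients is about 98% at the implied SD of 3.12 days. Only on the hypothetical reading that 1078 counts randomised patients does power in that group depend on positivity, and even then the primary analysis of all confirmed patients has more room. A sample-size statement whose conclusion does not follow from its inputs still has to be corrected, because the plan's only total target depends on it.

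**What to change.** In Section E, and in Section 6 of the final protocol, replace the single total with one labelled chain, with every value taken from the sponsor's 12/17/20 calculation:

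1. At least 204 Black or Latino patients with confirmed COVID-19 per arm, for 90% power to detect a 1-day mean difference in DAOH, with the SD stated and two-sided alpha 0.05.
2. The Black or Latino share among confirmed patients (61% as now stated).
3. The confirmed total, 408 divided by that share (669 if 61%).
4. Any loss allowance.
5. The assumed positivity rate.
6. The randomised total, which is the confirmed total (after any loss allowance) divided by positivity.

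Then label 1078 as confirmed or randomised, as those records show. The back-solved 62%, 69% and 38% should not be written in unless the records show that they were planning assumptions. If 1078 confirmed patients was the intention, correct the share, or the per-arm number and power, instead.

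The cost is wording and stated figures only: no extra patients and no change to recruitment. The one small drawback is that a stated figure may look less favourable once its inputs are disclosed.
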